## Planned Statistical Analyses

All analyses will be conducted **separately within each cohort** (Neurological and MSK), by original randomised allocation (intention-to-treat). Two-sided tests with  $\alpha = 0.05$  will be used throughout.

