#### 6. Safety Analyses

- **Adverse events:** Number and proportion of participants experiencing any AE and serious AE in each arm.
- Comparison by arm via  $\chi^2$  tests; descriptively summarised by severity and relatedness.

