## 5 STUDY DESIGN and METHODS of DATA COLLECTION AND DATA ANALYSIS

Type: Parallel, two-cohort (Neurological vs MSK), two-arm randomized controlled trial

- Arms (within each cohort):
  1. Usual-care physiotherapy only
  2. Combined ReHabGame + usual-care

Allocation: 1:1 randomisation, stratified by baseline severity (high vs low) within each cohort

- Blinding:
  - Outcome assessors blinded to group assignment

- Participants & therapists unblinded (interventions are overt)
- Duration: 6–8 weeks of intervention (2 sessions/week) + 4-week follow-up
- Sample size: 23 per arm per cohort (46 per cohort; 92 total), allowing ≈20% attrition.

Domain	Instrument & Timing
Demographics & History	Structured questionnaire at Week 0 (age, sex, diagnosis, time since onset/surgery, comorbidities)
Primary Outcomes	- Neurological: Fugl–Meyer Assessment (upper extremity) at Weeks 0, 8- MSK: SPADI at Weeks 0, 8
Secondary Outcomes	- Neurological: Barthel Index at Weeks 0, 8- MSK: DASH, pain VAS, goniometric ROM at Weeks 0, 8
Interim Metrics	At Week 4 for all: SUS, engagement survey, adverse-event checklist, quick FMA-UE subset (neuro) or SPADI re-test (MSK), Kinect snapshot metrics
Follow-up Metrics	At Week 12: SUS, engagement survey, adverse-event update, optional brief functional check
Motion-Tracking Data	Automatically logged each session via Kinect: range of motion, smoothness (jerk), repetition count, completion time, accuracy
Session Adherence	PDF session log (date, duration, pain VAS, issues) maintained by participant; automatically generated session report PDFs summarising movement metrics
Qualitative Feedback	Semi-structured interview or written feedback at end of Week 8 (usability, barriers, facilitators, motivation)
Safety Monitoring	Adverse events recorded at every session and via AE checklist at Weeks 4, 8, 12; severity and relatedness noted

All analyses conducted separately within each cohort on an intention-to-treat basis,  $\alpha = 0.05$  two-sided.

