### 3. Secondary & Repeated-Measures Analyses

- **Continuous outcomes** (Barthel, DASH, Pain VAS, ROM, SUS, engagement scores):
  - ANCOVA at Week 8 as above
  - **Mixed-effects linear models** for repeated measures (Weeks 0, 4, 8) with fixed effects for time, arm, and timexarm; random intercepts for participants
- **Categorical safety outcomes:** AE counts compared via  $\chi^2$  or Fisher's exact tests

4. **Motion-Tracking Metrics**
  - o Compare mean ROM, smoothness, completion time, and accuracy at Weeks 4 and 8 using ANCOVA, adjusting for baseline Kinect metrics
5. **Exploratory Analyses**
  - o **Cost/resource use:** descriptive comparison of therapist time and equipment costs per participant (t-tests or nonparametric equivalents)
  - o **Qualitative data:** thematic analysis of interviews to identify barriers/facilitators; representative quotes to illustrate key themes
6. **Missing Data**
  - o **< 5% missing:** complete-case analysis
  - o **≥ 5% missing:** multiple imputation by chained equations (20 datasets) including baseline covariates and outcomes
  - o **Sensitivity:** per-protocol analysis (≥ 75% sessions attended)
7. **Safety Review**
  - o AE rates summarised by arm; reviewed by an independent Data Monitoring Committee at midpoint (after ~50% complete)

All statistical programming and reporting will be done in R ( $\geq 4.0$ ), with scripts version-controlled for reproducibility.

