### **7.2.1 Size of sample**

Allocated as follows:

- o Per cohort: 46 participants
- o Per arm (1:1): 23 participants
- o Expected completers per arm:  $\geq 18$  participants
- o Total completers:  $\geq 72$  participants

This sample size is not powered for definitive hypothesis testing but is sufficient to:

1. Estimate recruitment, retention, and adherence rates with acceptable precision.
2. Generate variance estimates for the primary outcomes (FMA-UE in the Neurological cohort; SPADI in the MSK cohort) to inform sample-size calculations for a future definitive trial.

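### Adverse events fall under the cohort-separate rule, so no overall safety estimate on the 46 participants allocated to the combined arm is planned

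*Protocol*

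**What the plan says.** Two statements set the unit of analysis. Section 5 closes its design table with "All analyses conducted separately within each cohort on an intention-to-treat basis". The opening of Planned Statistical Analyses gives the same rule for all analyses, with two-sided α = 0.05.

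Safety is a numbered item under each statement:

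- Planned Statistical Analyses, item 6, asks for "Number and proportion of participants experiencing any AE and serious AE in each arm", with a comparison by χ² test.
- Section 5, item 7, has "AE rates summarised by arm; reviewed by an independent Data Monitoring Committee at midpoint".

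Neither item says whether the arm is taken within or across cohorts. Neither is exempted from the general rule, and no other section plans a pooled or cohort-stratified safety summary. The planned 95% confidence intervals are for feasibility rates and adjusted mean differences, not for adverse events.

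The third exploratory aim in section 4.1, on whether combined therapy adds risk, carries no cohort qualifier. The committee's review in item 7 of Planned Statistical Analyses is triggered by half of all participants completing Week 8, again without reference to cohort.

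**The concern.** Separate analysis is natural for efficacy, because the primary outcomes are different scales (FMA-UE and SPADI). That reason does not carry over to safety. The endpoint (any adverse event, any serious one), the checklist and its timing, the device and the game schedule are common to both cohorts. The anticipated physical risks in section 8.1 are described for all participants together.

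Section 9 calls the system a research prototype. For such a device an early trial's most useful safety output is how large a risk the data can still allow. If the rule is applied as written, that question is answered only on groups of 23, and the incremental-risk aim gets two imprecise answers with no overall one.

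**Working it through.** **Inputs.** The sample size is "23 per arm per cohort (46 per cohort; 92 total), allowing ≈20% attrition" (section 5), with allocation "1:1 randomisation, stratified by baseline severity (high vs low) within each cohort". The level is 0.05 two-sided. The protocol gives no expected adverse-event rate and no safety bound, so the event counts and risks below are assumptions.

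**1. The protocol's own counts.** 23 × 2 = 46 per cohort and 46 × 2 = 92 in total. With 20% attrition, 23 × 0.8 = 18.4, so at least 18 completers per arm, and 18 × 4 = 72. These match section 7.2.1. The combined arm across cohorts is 23 + 23 = 46.

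**2. No serious events in the combined arm.** The exact two-sided 95% upper limit is 1 − 0.025^(1/n).

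- n = 23: 14.8%
- n = 46: 7.7%
- Ratio: 1.92

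The ratio hardly depends on the choices made:

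- One-sided 95% limits, 1 − 0.05^(1/n): 12.2% against 6.3% (1.94).
- Completers only, 18 against 36: 18.5% against 9.7% (1.90).
- Using the 108 recruits named in section 7.2, so 108/4 = 27 against 54: 12.8% against 6.6% (1.93). That figure conflicts with 92, but the conflict does not affect this point.

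**3. Some serious events, at the same rate in both cohorts.** The exact (Clopper-Pearson) upper limit is the 97.5% point of Beta(x + 1, n − x).

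| Per cohort | Limit | Overall | Limit | Ratio |
|---|---|---|---|---|
| 1/23 | 21.9% | 2/46 | 14.8% | 1.48 |
| 2/23 | 28.0% | 4/46 | 20.8% | 1.35 |

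**4. Difference between arms, any adverse event.** For assumed risks of 30% and 15%, the 95% half-width is 1.96 × √[(0.30 × 0.70 + 0.15 × 0.85)/n].

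- n = 23 per arm: 1.96 × √(0.3375/23) = 23.7 points
- n = 46 per arm: 1.96 × √(0.3375/46) = 16.8 points

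**The case against.** The strongest case against is that separation is a reasoned choice. Section 2 describes the two conditions as having different pathophysiology. Eligibility differs, and cohort coincides with site: MSK only at the NHS hospital, neurological only at the private clinic. A pooled limit of 7.7% describes an average over the two populations and bounds neither cohort's own risk. This stands, and it is why the per-cohort tables must stay.

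A second objection is that extra safety tables belong in a statistical analysis plan. That holds for a supplementary treated-participants set. It does not hold for the scope rule: the protocol itself says that all analyses are by cohort, so a later plan adding an overall estimate would depart from it.

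Several stronger readings are tempting but not supported:

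- *Harm can never be assessed on all 46, or half the information is lost.* The safety items are ambiguous and do not forbid pooling. Per-cohort counts are planned and can be added by any reader.
- *The committee would see matching events only as isolated ones.* A single committee reviews the trial's safety data on a trial-wide trigger, so it would see both cohorts.
- *A planned bound on serious events is twice as wide as it need be.* The protocol plans no such bound. The limits here measure what the data could support, and a ratio near two needs zero or very few events.
- *Intention-to-treat materially dilutes the harm rate.* The documents give no number of never-starters. With an assumed 2 of 23, and no events among them, a 30% rate would read 0.30 × 21/23 = 27.4%. That change is small beside a half-width of 23.7 points. These participants may also have events under usual care.

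**Conclusion.** The point holds as a matter of scope and precision. As written, the cohort-separate rule covers adverse events, the word arm in the safety items is undefined, and no overall estimate is planned for an aim that is stated trial-wide.

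The gain from adding one is largest if no serious event occurs: an upper limit of 7.7% in place of 14.8%. It is more modest, a ratio of 1.35 to 1.5, if one or two events per 23 occur in each cohort. For the between-arm difference in any adverse event, the half-width falls from 23.7 to 16.8 points under the assumed risks. These figures use the 23 and 46 allocated and treat the average risk over the two populations as worth knowing alongside each cohort's own.

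This is a cheap improvement. The efficacy analyses are unaffected, and keeping safety by cohort is not itself an error.

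**What to change.** - In the opening of Planned Statistical Analyses and the closing statement of section 5, exempt adverse events from the cohort-only rule. They would be reported both by cohort and overall.
- In the safety items of both sections, say whether arm means within cohort or across cohorts. Keep the per-cohort tables.
- Add an overall comparison of any and serious adverse events stratified by cohort, for example a Mantel-Haenszel risk difference with 95% CI, and exact 95% limits for serious events in the combined arm.
- Give the Data Monitoring Committee the same summary at its midpoint review.
- Optional and minor: repeat the table for participants who had at least one session of their allocated treatment.

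The cost is about a sentence of wording and one or two tables, with no change to conduct or data collection. The downside is that the cohorts, which are also the sites, may have different event profiles that an overall figure would average. The retained per-cohort tables show this.

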### 1. Feasibility & Descriptive Statistics

- Recruitment, retention, and adherence rates: counts (%) with 95% CIs
- Session completion: mean  $\pm$  SD sessions attended per arm
- Data completeness: proportion of non-missing data per outcome

### 2. Primary Analyses

- ANCOVA with Week-8 score as the dependent variable (adjusting for baseline value, age, sex, and severity stratum); report the adjusted mean difference (95% CI) between arms.

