#### Analysis:

- Analysis of covariance (ANCOVA) with Week 8 score as dependent variable, adjusting for:
  1. Baseline score
  2. Age
  3. Sex
  4. Randomisation stratum (high vs low severity)
- Report adjusted mean difference at Week 8 with 95% CI and p-value

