## Feasibility Objectives

- Estimate **recruitment rate, retention rate, and data completeness** for each arm and cohort.
- Evaluate the acceptability of randomisation into **Combined ReHabGame + usual care** versus **usual care alone**.
- Generate preliminary estimates of **variance** in primary outcomes to inform sample-size calculations for a definitive trial.

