### 7.1.2 Cohort-Specific Inclusion Criteria

- **Neurological cohort:**
  1. Clinically diagnosed stroke, traumatic brain injury, or relapsing-remitting multiple sclerosis
  2. Upper-limb motor impairment: FMA-UE score 20–50 at baseline
  3.  $\geq 3$  months post-stroke or  $\geq 6$  weeks post-MS relapse
- **MSK cohort:**
  1. Diagnosed rotator cuff repair ( $\geq 6$  weeks post-op), adhesive capsulitis, or shoulder arthroplasty (< 6 months)
  2. Pain  $\leq 6/10$  on resting VAS
  3. Active shoulder elevation  $\geq 30^\circ$
  4. On a stable physiotherapy regimen ( $\leq 2$  sessions/week)

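### The primary ANCOVA ignores the diagnosis collected at Week 0 although each cohort pools conditions that plausibly recover at different rates: a possible loss of precision, not a bias

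*Protocol*

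**What the plan says.** The protocol states the primary analysis twice: under Planned Statistical Analyses (2. Primary Outcomes, Analysis) and in section 5 (2. Primary Analyses). Both give the same closed list of covariates, which section 5 words as "ANCOVA with Week-8 score as the dependent variable (adjusting for baseline value, age, sex, and severity stratum". The first names the last of these as "Randomisation stratum (high vs low severity". Section 5 has allocation "stratified by baseline severity (high vs low) within each cohort", and section 7.2.2 repeats this. No other stratification factor is named.

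Section 7.1.2 defines who is pooled. The neurological cohort takes "Clinically diagnosed stroke, traumatic brain injury, or relapsing-remitting multiple sclerosis", with a minimum time since stroke or MS relapse, no maximum, and no time window for brain injury. The MSK cohort takes rotator cuff repair from 6 weeks after operation with no upper limit, then "adhesive capsulitis, or shoulder arthroplasty (< 6 months". Capsulitis has no time limit.

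The section 5 data-collection table provides for a "Structured questionnaire at Week 0 (age, sex, diagnosis, time since onset/surgery, comorbidities". Neither diagnosis nor time since onset enters the strata or the primary model.

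The Feasibility Objectives in section 4.1 include preliminary variance estimates "in primary outcomes to inform sample-size calculations for a definitive trial", and section 7.2.1 repeats that purpose while saying that the trial is not powered for definitive testing.

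**The concern.** A baseline score and a high/low severity stratum describe a patient's status at one time. They need not describe how fast that patient would change over the next 8 weeks under usual care. A post-surgical shoulder and a frozen shoulder with the same SPADI may have different expected Week 8 scores, and so may a patient with MS and one with stroke. The time limits in section 7.1.2 suggest that the protocol itself regards time since the event as relevant.

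If diagnosis predicts Week 8 score beyond the planned covariates, leaving it out moves that predictable variation into the residual. This affects the precision of the Week 8 arm difference and the residual variance passed on to the definitive trial. Because the covariate list is fixed in the protocol, this is a stated choice and not a detail left to an analysis plan.

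**Working it through.** **The plan's own figure.** Section 7.2.1 expects at least 18 completers per arm and 72 in total. 23 × 0.8 = 18.4, rounded down to 18; 4 × 18 = 72. Both reproduce, so n = 36 completers per cohort is used below.

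**Assumptions not in the documents.** A 50/50 split of post-surgical and capsulitis patients in the MSK cohort; a SPADI SD of 18 within diagnosis after the planned covariates; and a natural 8-week difference d of 10, 15 or 20 points between the two groups that those covariates do not explain.

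**Residual variance when diagnosis is omitted.** With share p in one group, the inflation is 1 + p(1 − p)d²/18². At p = 0.5:
- d = 10: 1 + 25/324 = 1.08
- d = 15: 1 + 56.25/324 = 1.17
- d = 20: 1 + 100/324 = 1.31

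A 50/50 split gives the largest effect for a given d. At 80/20, p(1 − p) = 0.16 and d = 15 gives 1 + 36/324 = 1.11.

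**Width of the 95% CI.** With q covariates, Var(effect) = residual variance × (4/n) × (n − 3)/(n − q − 3), on n − 2 − q degrees of freedom.
- Planned model, q = 4: half-width at d = 0 is 2.042 × √(4/36 × 33/29) × 18 = 13.07. For other d, multiply by the square root of the inflation.
- One indicator added, q = 5: 2.045 × √(4/36 × 33/28) × 18 = 13.32, whatever d is.

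| d (points) | Planned, formula | With indicator, formula | Change | Simulated planned → with indicator | Change |
|---|---|---|---|---|---|
| 0 | 13.07 | 13.32 | +1.9% | 12.89 → 13.14 | +1.9% |
| 10 | 13.57 | 13.32 | −1.8% | 13.45 → 13.19 | −1.9% |
| 15 | 14.16 | 13.32 | −5.9% | 13.99 → 13.17 | −5.9% |
| 20 | 14.95 | 13.32 | −10.9% | 14.76 → 13.13 | −11.0% |

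The simulation used 2000 runs with 18 per arm.

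**Break-even.** The standard error falls once the term explains more than 1 − 28/29 = 3.4% of the planned model's residual variance. For the CI, the inflation must reach (13.32/13.07)² ≈ 1.039, so 0.25d² ≈ 0.039 × 324 ≈ 12.6 and d ≈ 7 points.

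**Validity.** A separate simulation (4000 runs per setting, 36 completers, stratified 1:1 allocation) let diagnosis and time since onset together explain 0 to 40% of the planned model's residual variance. The planned ANCOVA had mean error about 0 and 95% CI coverage of 0.95 to 0.96 throughout.

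**Consequence for a definitive trial.** If the omitted terms explain a share R² of the residual variance, the planned-model variance exceeds the adjusted one by 1/(1 − R²): 1.11 at R² = 0.1 and 1.25 at 0.2. For a difference of 0.5 planned-model SD at 80% power, 63 per arm falls to 57 and 51 respectively if the definitive trial adjusts. R² is assumed; the documents do not give it.

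**The case against.** The strongest reply is that nothing here is invalid. Natural recovery acts in both arms, randomisation protects the comparison, and this is a pilot without formal power. A reader might infer from the mixed case load that the treatment effect is biased by recovery stage. The documents do not support that, and the simulation shows no bias and nominal coverage.

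The size is also assumed. Below about 7 points the extra term costs precision, and at 10 points the gain only matches the loss at zero. This stands, and it is why the range and the null case are both shown.

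The larger variance is not wrong in itself. It is the correct one for a definitive trial with the same case mix and the same model, and too large only for one that adjusts for diagnosis. The protocol does not commit to either. On 30 residual degrees of freedom the 95% limits for the variance are about 0.64 to 1.79 times the estimate, so an 8% to 31% shift lies within sampling error. An adjusted variance could also be computed later from the collected data. All of this stands, and it keeps the point modest.

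Chance imbalance in diagnosis between arms and inflation of the residual variance are one effect seen from two sides. They should not be added together.

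It would be too strong to say that the Week 0 data go unused. The missing-data section puts all baseline covariates into the imputation model when 5% or more is missing, which can be read to include diagnosis. That does not bring diagnosis into the primary model.

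The remaining eligibility limits, such as FMA-UE 20 to 50, narrow the mix but do not remove it. Finally, section 7.1.1 requires no surgery in the past 3 months, while section 7.1.2 admits cuff repair from 6 weeks. If the first covers the index operation, the two conflict, and the range of recovery stages in the MSK cohort depends on how that is settled.

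**Conclusion.** The point holds as a proportionate improvement, not as an error that invalidates the analysis. The primary model omits a collected baseline factor that plausibly predicts change. The cost is possible loss of precision and a variance estimate that fits only a definitive trial with the same mix and model.

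For SPADI, with the assumed split, SD and 10 to 20 point difference, the residual variance is 8% to 31% larger than it need be, and one indicator narrows the 95% CI by about 2% to 11%. With no difference it widens the CI by about 2%. A less even split gives smaller gains. For FMA-UE the gain cannot be sized from the material at hand. The worst-case cost of about 2% applies there too, because it comes only from the lost degree of freedom.

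A reader might also infer that randomisation needs further strata. That does not follow: three diagnoses by two severity levels leave 46/6 ≈ 7.7 participants per cell, so covariate adjustment is more practical.

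**What to change.** In both statements of the primary analysis (Planned Statistical Analyses, and section 5 item 2), add one Week 0 term per cohort, named before any outcome data are seen:
- MSK: post-surgical versus adhesive capsulitis.
- Neurological: MS versus stroke or traumatic brain injury.

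Keep baseline score, age, sex and severity stratum. One term is enough: adding two diagnosis indicators and time since onset together would need an R² of about 0.10 to break even at 36 completers, against about 0.03 for one. The MSK indicator does not capture differences in time since surgery among operated patients.

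Report the residual variance with and without the added term, so that the definitive trial can use the figure matching its own model and case mix.

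Separately, reconcile sections 7.1.1 and 7.1.2 on recent surgery, so that the MSK population is unambiguous.

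The cost is one sentence in each place and one degree of freedom per cohort, with no new data. The downside is a CI about 2% wider if diagnosis turns out not to be prognostic.

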### 3. Secondary & Repeated-Measures Analyses

- **Continuous outcomes** (Barthel, DASH, Pain VAS, ROM, SUS, engagement scores):
  - ANCOVA at Week 8 as above
  - **Mixed-effects linear models** for repeated measures (Weeks 0, 4, 8) with fixed effects for time, arm, and timexarm; random intercepts for participants
- **Categorical safety outcomes:** AE counts compared via  $\chi^2$  or Fisher's exact tests

4. **Motion-Tracking Metrics**
  - o Compare mean ROM, smoothness, completion time, and accuracy at Weeks 4 and 8 using ANCOVA, adjusting for baseline Kinect metrics
5. **Exploratory Analyses**
  - o **Cost/resource use:** descriptive comparison of therapist time and equipment costs per participant (t-tests or nonparametric equivalents)
  - o **Qualitative data:** thematic analysis of interviews to identify barriers/facilitators; representative quotes to illustrate key themes
6. **Missing Data**
  - o **< 5% missing:** complete-case analysis
  - o **≥ 5% missing:** multiple imputation by chained equations (20 datasets) including baseline covariates and outcomes
  - o **Sensitivity:** per-protocol analysis (≥ 75% sessions attended)
7. **Safety Review**
  - o AE rates summarised by arm; reviewed by an independent Data Monitoring Committee at midpoint (after ~50% complete)

All statistical programming and reporting will be done in R ( $\geq 4.0$ ), with scripts version-controlled for reproducibility.

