	
 
○ Compare change in FMA-UE score from baseline to week 8 between arms
 
• MSK cohort: 
 
○ Compare change in SPADI score from baseline to week 8 between arms
 
 
 
 
Secondary Objectives: clinical outcomes
 
 
• Within each cohort, compare between-arm differences in: 
 
○ Adherence & Engagement: session attendance, System Usability Scale (SUS)
 
○ Functional Independence: Barthel Index (neurological), DASH (MSK)
 
○ Pain & ROM (MSK only): VAS pain, goniometric ROM
 
○ Motion-tracking metrics: accuracy, smoothness, range captured by Kinect
 
 
 
 
Exploratory Objectives
 
 
• Cost and resource use (therapist time, equipment) across arms
 
• Participant satisfaction and motivation (mixed-methods interviews)
 
• Barriers/facilitators to implementing gamified rehab
 

--	--

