### 3. Intervention Sessions (Weeks 1–8): Questionnaire at week 2, 4, 8 (**via the above Link**)

- Combined arm only; 2x/week, Weeks 1–8

Usual care only:

- o 30–45 min therapist-led physiotherapy per session
- o 2 sessions/week for 6–8 weeks (standardised protocol)
- **Combined care- Usual-care + ReHabGame:**
  - o 30–45 min Kinect-guided exercises per session.
  - o Real-time difficulty adaptation; metrics auto-logged.
  - o Both modalities, each 2x/week (on separate days or back-to-back).
  - o Each session is logged in the PDF format.

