#### Secondary Objectives

- Assess usability of the system in clinical environments
- Determine impact of personalized difficulty adjustment on engagement and adherence
- Analyse accuracy and reliability of motion-tracking data
- Explore participant perceptions of motivation and user experience
- Identify barriers and facilitators to adopting gamified rehab technologies

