## Secondary Research Questions

Within each cohort, how do the two arms compare on:

- **Functional independence:** Barthel Index (Neurological) or DASH (MSK)
- **Engagement & usability:** System Usability Scale (SUS) scores and engagement survey ratings at Weeks 4, 8, 12
- **Session adherence:** Number and proportion of prescribed sessions completed
- **Motion-tracking performance:** Changes in Kinect-derived metrics (range of motion, smoothness, accuracy)
- **Pain & ROM (MSK only):** Pain VAS and goniometric ROM

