### Difficulty Adjustment Logic

- At each session, the system spawns **three interactive virtual objects** within the participant's reach zone.
- The participant's ability to successfully **interact with or complete tasks involving these objects** determines the next session's difficulty level.
  - If the participant is **unable to interact with all three objects**, the difficulty is **automatically reduced to Level 0**, providing a simplified task setup with wider target zones and reduced motion requirements.
  - If the participant completes the interactions successfully, the difficulty level is **increased incrementally up to Level 5**, which includes:
    - Increased object speed
    - Reduced object size
    - More complex trajectories
    - More demanding spatial configurations

This **fuzzy logic-based scaling** allows for a responsive system that adjusts to moment-to-moment motor performance, thereby personalising therapy without requiring therapist intervention.

**No remote questionnaires or feedback sessions will be conducted unless the participant explicitly prefers to complete their follow-up session online.**

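### The planned Kinect ANCOVA needs a baseline that is never scheduled, and SUS is compared between arms although it has no Week 0 value and usual care has no defined system to rate

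*Protocol*

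**What the plan says.** **What is to be compared.** The Study Summary introduces its secondary objectives with "Within each cohort, compare between-arm differences in" and lists SUS and the Kinect movement metrics beneath. Section 4.1, Secondary Research Questions, asks "Within each cohort, how do the two arms compare on" and lists both again, timing SUS at Weeks 4, 8 and 12. Neither place names a method.

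**How.** Section 5, item 4 will "Compare mean ROM, smoothness, completion time, and accuracy at Weeks 4 and 8 using ANCOVA, adjusting for baseline Kinect metrics". Section 5, item 3 puts SUS into a Week 8 ANCOVA of the same form as the primary one, hence with a baseline value, and into a mixed model over Weeks 0, 4 and 8. Item 3 of Planned Statistical Analyses likewise sends continuous secondary outcomes, with SUS and motion tracking on its list, to the primary-type ANCOVA.

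**What is collected.** Item 3 of Study Timeline and Procedures gives the game sessions to the "Combined arm only; 2x/week, Weeks 1–8". The section 5 data table describes motion-tracking data as "Automatically logged each session via Kinect: range of motion, smoothness (jerk), repetition count, completion time, accuracy". The same table schedules, "At Week 4 for all: SUS, engagement survey, adverse-event checklist, quick FMA-UE subset (neuro) or SPADI re-test (MSK), Kinect snapshot metrics".

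**What the game does.** Under Difficulty Adjustment Logic, success with three virtual objects "determines the next session's difficulty level", on a scale from Level 0 to Level 5. Separately, the Secondary Objectives under Outcome Measures include: "Determine impact of personalized difficulty adjustment on engagement and adherence".

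**The concern.** The protocol has already fixed the model, the covariate and the time points, and its visit schedule does not supply the data. This is not detail that a statistical analysis plan could add later: a Week 0 capture cannot be recovered once treatment has begun.

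Four things follow if the text is kept.

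- The adjusted Kinect model cannot be fitted, so the analysis would be improvised after the data are seen.
- Usual-care participants would complete a usability scale with nothing defined to rate. Section 4 names usability in the overall aim of comparing the arms, so this affects a headline claim of the study.
- Session-logged accuracy and completion time depend on the level being played. Success makes objects faster, smaller and harder to follow, so a patient who improves can appear slower or less accurate.
- The missing-data rule (multiple imputation once 5% or more of an outcome is missing) has no exception for values that were never due. It could be read as calling for imputed usual-care values.

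The objective on personalised difficulty has a different fault. Every game user gets the adaptive algorithm, so there is no non-adaptive group against which to measure its impact.

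**Working it through.** The protocol gives no figure for this analysis, so there is none to reproduce. The check sets the schedule beside the models and then asks whether the arm effect can be estimated.

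**Step 1: what is scheduled.** Sources: Study Timeline items 1 and 3 to 6, section 4.1, the section 5 data table, section 6 (baseline assessments), and Appendix 2.

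| Measure | Week 0 | Week 4 | Week 8 | Week 12 |
|---|---|---|---|---|
| Kinect, combined arm | none listed | session logs and snapshot | session logs while sessions continue; no snapshot named | none listed |
| Kinect, usual care | none listed | snapshot | none named | none listed |
| SUS | none listed | section 4.1 and data table | section 4.1 only | section 4.1 and data table |

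The Week 0 visit lists a functional test, and the Week 8 visit repeats the baseline tests. Since Kinect is not among the baseline tests, Week 8 does not inherit it. Appendix 2 has a questionnaire at Weeks 2, 4 and 8 whose content is not described, but it too has no Week 0 entry.

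**Step 2: the Kinect model.** Per cohort there are 23 per arm, 46 in all (section 7.2.1). The model is

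outcome = b0 + b1·arm + b2·baseline + b3·age + b4·sex + b5·stratum (6 columns).

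Item 4 names only the baseline covariate. Age, sex and stratum are carried over from the primary ANCOVA as an assumption.

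| Data situation | Rows | Rank / columns | Arm effect estimable? |
|---|---|---|---|
| As written: no baseline value in either arm | 0 | – | no, model cannot be fitted |
| First game session used as baseline (combined arm only) | 23 | 5 / 6 | no |
| Week 4 snapshot for all, baseline term dropped | 46 | 5 / 5 | yes |
| Same snapshot at Week 0 and at the outcome visit, both arms | 46 | 6 / 6 | yes |

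In the second row the arm column equals the intercept, so one column is lost. Without age, sex and stratum it would be 2 of 3 columns, with the same conclusion.

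**Step 3: SUS.** Both the ANCOVA and the Week 0 term of the mixed model need a Week 0 score, and 0 of 46 are scheduled. A Week 0 score would mean nothing in either arm, because nobody has used the system by then. The data table asks everyone for SUS at Week 4 but does not say what usual-care participants rate.

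**Step 4: the missing-data rule.** Week 8 Kinect values are unscheduled for 23 of 46 = 50% of a cohort. If these count as missing, the 5% threshold is passed, with no observed usual-care values at that visit to inform the imputation.

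**Step 5: precision of a repaired comparison.** Section 7.2.1 expects at least 18 completers per arm (23 × 0.8 = 18.4).

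- Unadjusted: SE = √(2/18) = 0.333 SD. The difference detectable with 80% power at two-sided 0.05 is (1.960 + 0.842) × 0.333 = 0.93 SD.
- Baseline-adjusted: multiply by √(1 − r²). The protocol gives no correlation r, so a range is assumed: r = 0.3, 0.5, 0.7 gives factors 0.954, 0.866, 0.714 and detectable differences of 0.89, 0.81, 0.67 SD.

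**The case against.** The best defence is that this is a gap in the schedule. Naming baseline Kinect metrics in the analysis suggests that a Week 0 capture was meant and left off the visit list. Once it is added, the Week 8 repeat of baseline tests would carry it forward in both arms. That is a fair reading of intent, and it is why adding the capture is offered below as one remedy. It does not change the text, which no site could follow to obtain the covariate, and it does nothing for SUS.

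A reader might also infer more than the documents support:

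- *That usual-care participants never meet the system.* They have no ReHabGame sessions, but the data table schedules a Kinect snapshot and SUS at Week 4 for everyone, and Study Timeline item 4 does not limit the snapshot to one arm.
- *That no between-arm Kinect comparison is possible.* An unadjusted comparison at Week 4 is.
- *That adaptive difficulty spoils all Kinect data.* This is established only for metrics logged during play. The snapshot task is not described and may be a standard one.
- *That imputation will fabricate usual-care values.* The rule could be read that way, but the protocol does not say whether values never due count as missing.

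Finally, these are secondary outcomes in a pilot that section 7.2.1 says is not powered for definitive testing. That limits the severity, but does not make the specified analysis workable.

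**Conclusion.** The point stands in a limited form. The baseline-adjusted Kinect ANCOVA cannot be run as written: 0 of 46 baseline values are scheduled per cohort, and 0 of 23 usual-care values are named at Week 8. Only an unadjusted Week 4 snapshot comparison is supported. The SUS models lack their Week 0 value, and the between-arm SUS comparison has no interpretation while usual care has no defined system to rate. Session-logged accuracy and completion time are mixed up with difficulty level.

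This rests on reading the visit lists as complete and on ReHabGame sessions being confined to the combined arm. Appendix 2 does not split its exercise row by arm, but the Study Timeline does.

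It should be corrected, but it is not critical to the trial. The FMA-UE and SPADI analyses are unaffected, as is goniometric ROM, which is a separate measure taken at Weeks 0 and 8.

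**What to change.** 1. Remove SUS and session-logged Kinect metrics from the between-arm lists and models in the Study Summary, section 4.1, Planned Statistical Analyses item 3, and section 5 items 3 and 4. Report them by cohort for the combined arm only, as means with 95% CI, with Kinect metrics shown by difficulty level.
2. In both missing-data sections, state that usual-care participants are not imputed for these outcomes.
3. If a between-arm movement comparison is wanted, choose one of:
   - the Week 4 snapshot alone, with the baseline term deleted and the task described; or
   - the same standard-task snapshot in both arms at Weeks 0, 4 and 8, with Week 0 taken before randomisation, and the planned ANCOVA kept.
4. Separately, reword the personalised-difficulty objective as descriptive.

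Items 1, 2 and 4 cost only wording and the loss of between-arm claims that the data could not support. The first choice under item 3 needs no new visit content but gives up Week 8 and the gain from baseline adjustment. The second adds two short recordings per participant and a little device exposure in usual care. It also needs equipment at both sites: section 6 documents a supplied Kinect only for the neurological site, so availability for the MSK cohort should be confirmed.
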